2.1 PRIMARY OBJECTIVE

AIM: To assess the safety and efficacy of subcutaneous abatacept in an open-label trial of refractory JDM in 10 adults and children.

- **Hypothesis A: *Abatacept will be well-tolerated and safe in treatment–refractory JDM patients.*** For this, the NCI Common Terminology criteria version 4.0 June 2010 will be applied. Medical records will be reviewed for the 6 months prior to enrollment to obtain adverse events prior to beginning abatacept, which will be compared to any adverse events that develop after abatacept was initiated. Particular attention will be given to serious adverse events and infections. Patient evaluations will include: vital sign measurement, physical examination, and laboratory parameters for hematology and routine chemistries.
- **Hypothesis B: *Patients will clinically improve after treatment with abatacept.*** We hypothesize that at least 6 of 10 patients will meet the myositis preliminary definition of improvement after receiving 24 weeks of therapy with abatacept.

Definitions of improvement (DOIs) for clinical trials in IIM have recently been proposed by the IMACS Group (International Myositis Assessment and Clinical Studies) for adult and pediatric myositis utilizing six core set measures among five domains of myositis disease activity (38) (**see Appendix C**). They are:

- a) Physician global disease activity;
- b) Parent/patient global disease activity;
- c) Muscle strength, utilizing manual muscle strength testing (MMT8);
- d) Physical function assessment using the (Childhood) Health Assessment Questionnaire (CHAQ);
- e) Laboratory assessment using the most abnormal serum muscle enzyme level; and
- f) Extra-muscular disease activity using the Myositis Disease Activity Assessment Tool (MDAAT). (see section 14.0: assessment tools: description) (39)

For this clinical trial, the primary endpoint will be the published Definition of Improvement (DOI): 3 of any of the 6 core set measures improved by $\geq 20\%$, with no more than 2 of the core set measures worsening by $\geq 25\%$ (worsening measures cannot include the muscle strength). (Appendix D1) (38)

The PRINTO Group (Pediatric Rheumatology International Trials Organization) has developed and validated a core set of outcome variables for the evaluation of response to therapy in JDM. (40) (Appendix C)

The additional PRINTO core set activity measures are:

- 1) Childhood Myositis Assessment Scale is used as a measure of strength;

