	c. Has the patient had intolerance or an inadequate response to methotrexate at least 15 mg/week or 0.3 mg/kg or 15 mg/m ² / week for at least 3 months?
	d. Has the patient had intolerance or an inadequate response to mycophenolate mofetil at least 30 mg/kg/d or 1000 mg bid for at least 3 months?
	e. Has the patient had intolerance or an inadequate response to cyclophosphamide at least 1.0 mg/kg/d poor 500 mg/m ² /month IV for at least 3 months?
	f. Has the patient had intolerance or an inadequate response to oral tacrolimus for at least 3 months?
	g. Has the patient had intolerance or an inadequate response to cyclosporine at least 2.5 mg/kg/d for at least 3 months?
	h. Has the patient had intolerance or an inadequate response to IVIG at least 1.0 g/kg/month for at least 3 months?

	i. Has the patient had intolerance or an inadequate response to an anti-TNF agent (including Etanercept, Infliximab, Humira, etc) for at least 3 months?
	j. Has the patient had intolerance or an inadequate response to 2 infusions of Rituximab (375mg/m ² (for 4 doses), or 500 mg/m ² or 1000 mg for 2 doses)?
6	Considering 6a-6f, Does the patient have a moderately active disease (MD global VAS with a minimum value of 2,5 cm on a 10 cm scale plus another 2 other abnormal Core set Measures as listed above (7b-7f)
	a. Does the MD global VAS have a minimum value of 2.5 cm on a 10 cm scale
	b. Is the MMT-8 score no greater than 125/150
	c. Does the Patient/parent Global VAS have a minimum value of 2.0 cm on a 10 cm scale
	d. Does the CHAQ/HAQ disability index have minimum value of 0.25
	e. Is at least one of the muscles enzymes (including CK, aldolase, LDH, AST and ALT) elevated at a minimum level of 1.3 times the upper limit of normal. If more than one muscle enzyme is identified as being elevated and meeting the above guidelines, then the most abnormal will be selected and this enzyme will be the target enzyme followed to evaluate disease improvement or worsening.
	f. Does the Global extra-muscular disease have a score with a minimum value of 2 cm on a 10 cm VAS scale.
7	Is the prednisone dose stable for 4 weeks prior to the screening visit? (recommended dose ≤ 1.0 mg/kg/day)

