- Perform radiographic examination of chest

Some patients may wish to obtain screening labs at home and present the results at the screening visit. This would enable them to enter the intervention phase at the same visit as the screening visit. Results dated within 6 weeks prior to screening visit will be accepted to satisfy eligibility criteria.

All safety labs during the regular study visit may be completed at the home institution up to 10 days prior to the visit and reports sent to GW.

A re-screen protocol will be followed if a period of greater than 45 days elapses between the screening visit and start of treatment.

Visit 1/Week 0 (Intervention phase)

Visit 1(week 0) will occur 0- 45 days after all initial screening evaluations are concluded and the results of screening testing procedures are completed. The subject must remain in the clinic for 15 minutes following administration of study drug. The following evaluations/procedures will be performed at this visit.

- Review of inclusion/exclusion criteria
- NCI Common Toxicity Assessment
- Obtain vital signs (HR,BP,RR, oral temperature and weight, and if indicated, by history of shortness of breath or lung disease, pulse oximetry)
- Medical history and perform a full physical examination
- Collect urine sample for pregnancy test for females of child bearing potential prior to administration of study medication (where applicable)
- Core set activity measures: physician global activity, patient/parent global activity, manual muscle testing (MMT-8), CMAS, HAQ/CHAQ, MDAAT, muscle enzymes, CHQ PF-50/SF- 36, and Disease Activity Score (DAS)
- Myositis Damage Index (MDI): assessment of disease damage completed by the physician during physical examination.
- Physician global damage (VAS)
- Dermatology assessment: CDASI, MD Global Skin Activity + Damage (Optional)
- CDASI, photographs of skin rashes, periungual nailfold capillary assessment.

- Quality of life questionnaires: CHQ PF-50/SF- 36, Dermatology Life Quality Index (DLQI), PROMIS/fatigue, Peds QL fatigue
- Muscle MRI: bilateral thighs and pelvis, axial STIR and T1 images
- Plain radiographs for calcinosis for patients with calcinosis
- Obtain blood samples for Chem-20, GGT, CK, aldolase, LDH, CBC with diff., TSH, anti-thyroid antibodies, von Willebrand Factor antigen level, quantitative immunoglobulins (IgG, IgM, IgA), ANA, ENA, dsDNA, Lymphocyte flow cytometry (TBNK cells)
- Urinalysis

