Phone follow-up #7 (14 days (+/- 7 days after visit 4)

- Adverse events will be reviewed and recorded (NCI Common Toxicity criteria version 4.0).

Phone follow-up #8 (will occur 28 days (+/- 7 days) after visit 4.

- Adverse event will be reviewed and recorded.

Visit 5 (week 24) will occur 42 days (+/- 10) days after Visit 4 (End of Study Treatment or Early Termination)

- Review concomitant medication and query for adverse events and document in CRF.

- NCI Common Toxicity Assessment
- Obtain vital signs (HR,BP,RR, oral temperature and weight) and if indicated , by history of shortness of breath or lung disease, pulse oximetry)
- Medical history and perform a full physical examination
- Collect urine sample for pregnancy test for females of child bearing potential prior to administration of study medication (where applicable)
- Core set activity measures: physician global activity, patient/parent global activity, manual muscle testing (MMT-8), CMAS, HAQ/CHAQ, MDAAT, muscle enzymes, CHQ PF-50/SF- 36, and Disease activity score (DAS)
- Quality of life questionnaires: CHQ PF-50/SF- 36, DLQI , PROMIS/fatigue and Peds QL fatigue
- Myositis Damage Index (MDI): assessment of disease damage completed by the physician during physical examination. Physician global damage (VAS)
- Physician and patient/parent assessment of study outcome
- Dermatology assessment performed by Rheumatologist: CDASI, photographs of skin rashes, periungual nailfold capillary assessment
- Dermatology Assessment performed by Dermatologist: CDASI, MD Global Skin Activity + Damange (Optional)
- Prednisone taper may commence using a predetermined schedule (section 5) If the patient has achieved the Definition of Improvement (DOI) and is rated by the study physician as at least minimally improved..
- Muscle MRI: bilateral thighs and pelvis, axial STIR and T1 images
- Plain radiographs for calcinosis for patients with calcinosis
- Obtain blood samples for Chem-20,GGT, CK, aldolase, LDH, CBC with diff., TSH, anti-thyroid antibodies, von Willebrand Factor antigen level, quantitative immunoglobulins (IgG, IgM, IgA), ANA, ENA, dsDNA, Lymphocyte flow cytometry (TBNK cells) [**may be performed at home institution, up to 10 days before the visit date**]
- Collect research blood samples for Immunophenotyping (T, B cells and macrophages), gene expression and cytokine/chemokine analysis (see Section 3.1.h)
- Urinalysis
- Review log of medication self-administration

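### The target muscle enzyme in the primary endpoint may be run in different laboratories at baseline and week 24, so a permitted change of laboratory can create or hide a 20% improvement

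*Combined protocol and SAP*

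**What the plan says.** **The endpoint.** Section 2.1 defines the primary DOI on six core measures. At least three must improve by 20% or more, no more than two may worsen by 25% or more, and strength may not be among those that worsen. The fifth measure is "Laboratory assessment using the most abnormal serum muscle enzyme level". Under Section 4.1, criterion 6e, an enzyme counts towards entry when it is "elevated at a minimum level of 1.3 times the upper limit of normal". If several qualify, the most abnormal is chosen, and "this enzyme will be the target enzyme followed to evaluate disease improvement or worsening".

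**Where the blood is tested.** All of the following is in Section 7.1.

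- Visit 1 (week 0): "Obtain blood samples for Chem-20, GGT, CK, aldolase, LDH, CBC with diff., TSH, anti-thyroid antibodies" and further tests, with no remark about a home laboratory.
- Visits 2 to 5 (weeks 6, 12, 18 and 24): the item holding the chemistry panel, CK, aldolase and LDH carries the note "may be performed at home institution, up to 10 days before the visit date".
- A general sentence under screening: "All safety labs during the regular study visit may be completed at the home institution up to 10 days prior to the visit", with reports sent to the site.

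**What is not said.** Sections 7.1, 14.0 and 15.0 and Appendices C and D1 do not name a central laboratory, do not ask for the same laboratory at baseline and follow-up, and do not give the scale for percent change. Section 12.3 does ask that, where possible, the same physician examine a subject throughout. There is no counterpart for the laboratory.

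**The concern.** The endpoint turns a percent change into yes or no at 20%. If numerator and denominator come from two laboratories, any systematic difference between them enters that percent change in full. The plan has one enrolling centre (Section 4.0) and accepts residents of the United States or Canada (Section 4.1, criterion 4), so use of home laboratories is foreseeable. A patient tested at the site at week 0 and at home at week 24 has followed the protocol exactly.

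The enzyme is the only laboratory measure among the six. In an open-label, single-arm trial it is the component least open to expectation on the part of physician, patient or parent, so it is worth protecting.

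Core-set change is also one input to the week-12 dose offer and, through the DOI, to the steroid taper. The enzyme contributes to both but alone decides neither.

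**Working it through.** The plan gives no alpha, power or null rate for the 6-of-10 target, and no between-laboratory difference, so there is no figure of its own to reproduce. The check has four steps.

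**1. Threshold arithmetic.** Let k be the home reading divided by the site reading on the same sample (assumed range), and t the true proportional fall.

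- Observed improvement = 1 − k(1 − t).
- True fall needed to read as 20% improved = 1 − 0.80/k.
- True rise needed to read as 25% worse = 1.25/k − 1.

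| k (assumed) | True fall needed | A true 25% fall reads as | True rise that reads as 25% worse |
|---|---|---|---|
| 0.80 | 0% | 40.0% | 56.2% |
| 0.90 | 11.1% | 32.5% | 38.9% |
| 1.00 | 20.0% | 25.0% | 25.0% |
| 1.10 | 27.3% | 17.5% | 13.6% |
| 1.20 | 33.3% | 10.0% | 4.2% |

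At k = 0.80 an improvement is created from nothing. At k = 1.10 a real 25% fall is hidden. With one laboratory, k = 1 and the distortion disappears.

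**2. When the enzyme decides the call.**

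- *Improvement count.* The enzyme is the third improvement only if exactly two of the other five improve. If each improves independently with probability q, the chance is 10·q²(1 − q)³: 20.5% at q = 0.2, 30.9% at 0.3, 34.6% at 0.4 and 31.2% at 0.5. Independence is an assumption.
- *Worsening limit.* Two worsened measures are allowed. A false enzyme worsening breaks the limit only as the third, and the patient must still have three improved. All six measures must then split three improved and three worsened.

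**3. Random differences in place of a fixed k.** Let w be the within-laboratory SD on the log scale and b the SD of ln k. With no true change, P(reads at least 20% improved) = Φ(ln 0.80 / √(2w² + b²)). The chance of missing a true 30% fall is 1 − Φ((ln 0.80 − ln 0.70) / √(2w² + b²)).

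| w | b | False 20% improvement | True 30% fall missed |
|---|---|---|---|
| 0.10 | 0 | 0.057 | 0.173 |
| 0.10 | 0.10 | 0.099 | 0.220 |
| 0.10 | 0.20 | 0.181 | 0.293 |
| 0.20 | 0 | 0.215 | 0.318 |
| 0.20 | 0.20 | 0.260 | 0.350 |

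**4. Effect on the responder rate.** Take q = 0.4, no true enzyme change, every patient switching, and the worsening limit ignored. The rate is P(at least 3 of the other 5) + P(exactly 2) × P(false improvement) = 0.317 + 0.346 × P(false improvement).

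- w = 0.10: 0.337 with one laboratory, 0.352 at b = 0.10, 0.380 at b = 0.20. P(at least 6 of 10) is 0.081, 0.097 and 0.135.
- w = 0.20: 0.392 with one laboratory, 0.407 at b = 0.20. P(at least 6 of 10) is 0.153 and 0.179.

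The average gain is thus at most 0.380 − 0.337 = 4.3 percentage points in these scenarios, under half a patient in ten.

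**The case against.** The strongest reply is that the switch may not happen. The general safety-laboratory sentence could be read to cover week 0, and Section 3.0 lets patients with home screening results start treatment at the same visit, so some may use one home laboratory throughout. A Manual of Operations is cited in Section 12.2 but is not among the documents, and it may hold a laboratory rule. The study is small and exploratory, and Section 15.0 concedes that it lacks power. Different home laboratories would mostly add noise in both directions. All of this limits the size of the problem. It does not close the gap, because the text leaves the choice of laboratory to chance, and a rule that shapes the primary endpoint belongs in the protocol.

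Four stronger readings are tempting, and the documents do not support them.

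- A reader might infer that a ratio of 1.25 costs a patient the DOI through false worsening. Outside the three-three split it does not. An upward shift matters mainly by hiding improvement.
- A reader might infer that the DOI applies to the raw value. The scale is unstated. Criterion 6e uses multiples of ULN, but only for entry and choice of enzyme.
- A reader might take the ratio of two ULNs as k. Reference limits can differ while the same sample reads alike. If two laboratories agree but their ULNs are 200 and 250 U/L (assumed), value/ULN changes by 200/250 = 0.80 or 250/200 = 1.25 with no real change. Rescaling is therefore not a safe repair by itself.
- A reader might infer that the enzyme drives treatment decisions. The taper also needs improvement ratings (Sections 5.0 and 7.1). For the week-12 offer, the Synopsis and Sections 6.2 and 7.1 add a physician rating that Sections 3.0 and 8.0 omit, and these passages must be reconciled. Sections 3.0 and 7.1 also admit the PRINTO measures, which contain no enzyme (Appendix C).

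**Conclusion.** The concern holds as a permitted and avoidable source of error in a thresholded primary endpoint. It does not show that the result will be biased, or in which direction. The textual gap is certain: no laboratory rule and no stated scale. The size rests on an assumed k.

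Differences of about 10% move patients near the threshold, and a ratio of 0.80 creates an improvement outright. The patient's call changes only when exactly two other measures improve, roughly 20% to 35% of patients under the stated assumptions, or in the rare three-three split. The average effect is modest, but with ten patients and a target of six, one changed call is 1/10, or 10 percentage points, and can decide whether the target is met. The remedy is cheap enough that the plan should be changed.

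**What to change.** **In Section 7.1:** require each patient's target enzyme to be run in one laboratory at week 0 and at every visit where DOI or core-set change is assessed, at minimum weeks 0, 12 and 24. Drawing it at the site visit is the simplest way. Keep the home-laboratory permission for the other safety tests, and say whether the general sentence covers week 0.

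**In the case report form:** record the laboratory and its ULN with each enzyme value.

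**In Section 15.0 and Appendix D1:** state whether percent change uses raw values or multiples of ULN. Where a patient's laboratories differ, flag the patient in the DOI listing and report DOI in two sensitivity analyses: on value/ULN, and with the enzyme counted as not improved. Two are needed because value/ULN can itself create false change.

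**Cost:** a few sentences and two data fields. Patients already attend in person, and research and drug-level blood is already collected at weeks 0, 12 and 24. The volumes in Appendix E already include the enzymes. For children at week 6, Table 2 gives 2.5 + 1.5 + 1.0 + 0.6 + 5.0 + 3.0 + 1.0 = 14.6 mL, the total in Table 2a, of which CK, aldolase and LDH are 9.0 mL. The downside is that patients lose home testing for this one tube or must keep to one laboratory.

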7.2 Laboratory Sample Collection

In case staff at the GW-MFA unable to get a reliable venous access for blood sample, the subject will be taken to the George Washington University Hospital to undergo ultrasound guided phlebotomy. The sample will then be carried to [name] location and processed there as per protocol.

8.0 DOSE MODIFICATION

The dose of abatacept will remain constant until week 12. For patients not improving with therapy by at least 5% on at least 3 of 6 core set measures at week 12, they would be offered the opportunity to increase their dose of treatment to abatacept 212 mg (87.5 + 125 mg) for subjects with body weight \geq 50 kg or to abatacept 137.5 mg (87.5 mg+ 50 mg for subjects with body weight of < 50 kg) weekly subcutaneously, or to continue on their present dose.

9.0 DISCONTINUATION OF SUBJECTS

Subjects in this study may be discontinued for any of the following reasons:

- Severe allergic reaction to the study medication
- Participation in another investigational drug study
- Any medical condition which, in the opinion of the investigator, warrants discontinuation from the study for the safety of the patient, either as a cause of the study drug or Protocol violations, including non-compliance or inability to perform protocol-required procedures
- Voluntary withdrawal (withdrawal of consent)
- Pregnancy
- Instruct WOCBP to contact the investigator or study staff immediately if they suspect they might be pregnant (e.g., missed or late menstrual period) at any time during study participation. Institutional policy and local regulations should determine the frequency of on-study pregnancy tests for WOCBP enrolled in the study.
- The investigator will notify BMS if a study subject becomes pregnant.
- Loss of ability to freely provide consent through imprisonment or involuntary incarceration for treatment of either a psychiatric or physical (e.g., infectious disease) illness.
- If 3 or more patients develop a serious adverse event thought to be related to study drug, no new patients will be enrolled into the study until the adverse events have been reviewed by the Medical Safety Officer and/or Data Safety Monitoring Board.

Criteria for Disease Worsening (Appendix F):

Criteria for disease worsening in a clinical trial, by which patients could be termed treatment failures and offered alternative therapies, were preliminarily defined by IMACS. They will be incorporated into this trial and include:

- Physician global worsening of ≥ 2 cm on the 10 cm visual analog scale (VAS) and a worsening of the manual muscle testing by $\geq 20\%$, or
- Global extra muscular organ disease activity (a composite of constitutional, cutaneous, skeletal, gastrointestinal, pulmonary and cardiac activity) worsening by ≥ 2 cm on a 10 cm VAS, or
- 3 of any 6 IMACS core set activity measures worse by $\geq 30\%$.

In order to be classified as “worsening” in this trial, subjects will have to meet the above criteria and be classified by the physician as at least moderately worse (on the Assessment of Study Outcome form). It was also noted by IMACS that significant worsening in cardiac, pulmonary (interstitial lung disease) or GI organs (dysphagia or vasculitis), which, based on the opinion of the treating protocol physician, requires alternate therapy, should be considered as alternate worsening criteria, potentially leading to patients being removed from a trial or considered treatment failures.

All subjects who leave the trial after receiving study drug, regardless of cause, are recommended to obtain a termination evaluation prior to study termination. All patients receiving at least one dose of abatacept will be encouraged to remain in the trial and complete all study visits and phone follow-up evaluations to continue to assess safety.

Continuation of subjects after a serious adverse-event will be based on discussions between the Principal Investigator and Medical Safety Officer and/or Data Safety Monitoring Board. If 3 or more patients develop a serious adverse event thought to be related to study drug, no new patients will be enrolled into the study until the adverse events have been reviewed by the Medical Safety Officer and/or Data Safety Monitoring Board.

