- Collect blood samples prior to the injection at Week 24 for PK and immunogenicity assessment
- Prednisone taper may commence using a predetermined schedule (section 5) if the patient has achieved the Definition of Improvement (DOI) and is rated by the study physician as at least minimally improved.
- Administer dose of study medication (abatacept) and observe after the injection for at least 15 minutes
- Patient terminates study enrollment and all study supplies are returned, or patient will continue on open-label extension: schedule and instruct the subject to return for the next visit

- An open label extension phase will be offered for up to 6 months for patients meeting the definition of improvement and who are rated by their study physician as at least minimally improved.
- If the subject chooses not to continue to be in the open label extension phase of the trial, the subject will be referred back to his/her local rheumatologist for further care. Subject terminates study enrollment and all study supplies are returned
- Subjects will receive their last injection of abatacept at week 24 even if they do not want to continue in the open label extension phase of the trial

Open label extension Visit (will occur within 6 months of visit 5)

An open label extension phase of up to 6 months duration will be offered to all patients meeting the definition of improvement and who are also rated as at least minimally improved from the baseline visit (visit 1). Patients must commit to at least one follow-up visit within 6 months of visit 5, which will be at their own expense for travel and testing costs. At each follow-up visit, the following will be performed:

- Review concomitant medication and query for adverse events and document in CRF.
- NCI Common Toxicity Assessment
- Obtain vital signs (HR,BP,RR, oral temperature and weight) and if indicated , by history of shortness of breath or lung disease, pulse oximetry)
- Medical history and perform a full physical examination
- Collect urine sample for pregnancy test for females of child bearing potential prior to administration of study medication (where applicable)
- Core set activity measures: physician global activity, patient/parent global activity, manual muscle testing (MMT-8), CMAS, HAQ/CHAQ,MDAAT, muscle enzymes, CHQ PF-50/SF- 36, and Disease activity score (DAS), physician global damage (VAS)
- Physician and patient/parent assessment of study outcome

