APPENDIX D1.

IMACS definition of minimal clinical improvement, PRINTO definition of minimal, moderate, and major improvement and PRINTO criteria of inactive disease**

IMACS definition of minimal improvement	PRINTO definition of minimal improvement	PRINTO definition of moderate clinical improvement	PRINTO definition of major clinical improvement	PRINTO definition of inactive disease
≥ 20% of improvement in at least 3 of 6 core set measures, with ≤ 2 of the remaining worsening by > 25% (muscle strength cannot worsen)	≥ 20% of improvement in at least 3 of 6 core set measures, with ≤ 1 of the remaining worsening by ≥ 30% (muscle strength cannot worsen).	≥ 50% of improvement in at least 3 of 6 core set measures, with ≤ 1 of the remaining worsening by ≥ 30% (muscle strength cannot worsen).	≥ 70 of improvement in at least 3 of 6 core set measures, with ≤ 1 of the remaining worsening by ≥ 30% (muscle strength cannot worsen).	At least 3 of 4 criteria: CMAS ≥ 48; MD global Activity VAS ≤ 0.5 cm; CK ≤ 150; MMT ≥ 78.

*IMACS, International Myositis Assessment and Clinical Studies Group

**PRINTO, Pediatric Rheumatology International Trials

References:

**Rider LG, Giannini EH et al. International consensus on preliminary definitions of improvement in adult and juvenile myositis. International Myositis Assessment and Clinical Studies Group. Arthritis Rheum. 2004 Jul;50(7):2281-90. Review.

**Ruperto N, Pistorio A et al. The Paediatric Rheumatology International Trials Organisation provisional criteria for the evaluation of response to therapy in juvenile dermatomyositis. Arthritis Care Res (Hoboken). 2010 Nov;62(11):1533-41

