APPENDIX F ACTION PLAN FOR TREATMENT OF WORSENING OF DISEASE:

Criteria for disease worsening in a clinical trial, by which patients could be termed treatment failures and offered alternative therapies, were preliminarily defined at an IMACS Workshop. These criteria will be incorporated into this trial.

. In order to be classified as “worsening” in this trial subjects will have to meet the following criteria:

(1) Physician global worsening of ≥ 2 cm on the 10 cm visual analog scale (VAS) and a worsening of the manual muscle testing by $\geq 20\%$, or

(2) Global extra muscular organ disease activity (a composite of constitutional, cutaneous, skeletal, gastrointestinal, pulmonary and cardiac activity) worsening by ≥ 2 cm on a 10 cm VAS, or

(3) 3 of any 6 IMACS core set activity measures worse by $\geq 30\%$. And

(4) Subjects will have to meet the above criteria and be classified by the investigator as at least moderately clinically worse.

Patients who improve by less than 5% in at least 3 of 6 core set measures by week 12, will be considered to be not improved : These patients may be offered higher dose therapy at 212 mg (87.5 + 125 mg) for subjects with body weight ≥ 50 kg or 137.5 mg for subjects with body weight < 50 kg abatacept weekly.

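### A patient can meet the primary improvement definition at week 24 and also be classed as worsening, or meet it after rescue therapy, and the plan has no rule for counting such a patient

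*Combined protocol and SAP*

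**What the plan says.** **Response.** Section 2.1 states that "the primary endpoint will be the published Definition of Improvement (DOI): 3 of any of the 6 core set measures improved by" at least 20%, "with no more than 2 of the core set measures worsening by" 25% or more, and muscle strength may not be among the worsened measures. Appendix D1 gives the strength condition as "muscle strength cannot worsen" and sets the limit for the other measures at more than 25%. Neither text caps how far the two tolerated measures may worsen, and neither asks for a physician rating of change.

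**Worsening.** Section 9.0 introduces "Criteria for disease worsening in a clinical trial, by which patients could be termed treatment failures and offered alternative therapies". There are three branches:

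1. physician global worse by at least 2 cm and manual muscle testing (MMT) worse by at least 20%;
2. extra-muscular activity worse by at least 2 cm;
3. three of the six core measures worse by at least 30%.

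Appendix F adds a condition: "Subjects will have to meet the above criteria and be classified by the investigator as at least moderately clinically worse".

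**What follows worsening.** Section 9.0 says that "All patients receiving at least one dose of abatacept will be encouraged to remain in the trial and complete all study visits". Section 5.0 allows a corticosteroid increase when disease worsens. Section 15.0 analyses by intention to treat, whatever the compliance with therapy or protocol. It does not mention worsening, treatment failure or alternative therapy.

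**The extension.** Section 7.1 offers it to "patients meeting the definition of improvement and who are also rated as at least minimally improved from the baseline visit", so there a physician rating is added to the DOI. The primary endpoint has no such addition.

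**The concern.** One part of the plan decides who improved and another decides who worsened, and nothing links them. If both labels can fall on the same patient, the headline count may include someone the investigator rates as moderately worse. It may also credit abatacept with a response obtained after another treatment was added. In a single open-label arm with a 6-of-10 target, both routes can only raise the count. Without an advance rule, the decision would be taken once the open-label results are known.

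**Working it through.** The target of at least 6 of 10 is a postulate with no null rate, alpha or power, so there is no derivation to reproduce. The check is whether the two rules can be true together.

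**Assumption.** Changes are measured from baseline under both rules. Section 14.0 makes baseline the reference for the physician's outcome rating; Section 9.0 names no reference visit for the three branches.

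**Branch 2 and the DOI: they overlap.** A 2 cm rise on a 10 cm scale requires a baseline b of at most 8 cm, so the relative worsening 2/b is at least 2/8 = 25%. It therefore uses exactly one of the two tolerated worsenings. One more is allowed, and three of the other measures can still improve.

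An illustrative patient:

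| Measure | Baseline | Week 24 | Change |
|---|---|---|---|
| Patient global | 5 | 4 | 1/5 = 20% better |
| CHAQ | 1.25 | 1.0 | 0.25/1.25 = 20% better |
| Enzyme | 500 | 400 | 100/500 = 20% better |
| MMT-8 | – | – | unchanged |
| Extra-muscular | 2 cm | 5 cm | +3 cm, 3/2 = 150% worse |
| Physician global | 4 cm | 6 cm | 2/4 = 50% worse |

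Three measures have improved, two have worsened and strength is unchanged, so the DOI is met under both Section 2.1 and Appendix D1. The extra-muscular rise exceeds 2 cm. With a rating of moderately worse, the patient is also classed as worsening. The baseline values satisfy the activity requirement in inclusion criterion 6.

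**Branch 1 and the DOI: a narrow overlap.** Branch 1 needs MMT worse by at least 20%; the Section 2.1 wording excludes MMT worse by 25% or more. The overlap is therefore MMT worse by 20% to less than 25%. For example, from a physician global baseline of 5 cm: physician global 40% worse (+2 cm), MMT 22% worse, three other measures 25% better. If Appendix D1 means that strength may not worsen at all, this overlap disappears.

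**Branch 3 and the DOI: no overlap at the same visit.** Three measures worse by at least 30% are also three worse by at least 25%, and 3 > 2.

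An enumeration over ten levels of change per measure, with assumed 5 cm baselines for physician and extra-muscular global, agrees: combinations meeting both rules exist for branch 2 on either strength wording, for branch 1 on the Section 2.1 wording only, and never for branch 3.

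**Across visits.** A patient may worsen at week 6, 12 or 18 by any branch, receive alternative therapy (Section 9.0) or more corticosteroid (Section 5.0), and meet the DOI at week 24. Under Section 15.0 as written, this patient counts as a responder.

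**Effect of one patient** (exact Clopper-Pearson 95% intervals):

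- 6/10 = 60% (26.2% to 87.8%), target met;
- 5/10 = 50% (18.7% to 81.3%), target missed.

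**Illustration, with rates assumed rather than taken from the documents.** P(X ≥ 6) = Σ C(10,k) p^k (1−p)^(10−k), summed over k = 6 to 10. If the DOI rate is 60%, P = 63.3%. If 5 of those 60 percentage points are patients who would be recounted, p = 55% and P = 50.4%. If 10 points are, p = 50% and P = 37.7%.

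**The case against.** The DOI is a published composite, and tolerating two worse measures is one of its properties. The worsening criteria serve a different purpose: deciding when alternative therapy may be offered. Requiring the two to exclude each other is a design preference. This stands, and it is why the unmodified count should also be reported.

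The secondary endpoints would expose the illustrative patient. Enzyme is not a PRINTO core measure, so on the values given only two improvements count there. In Appendix D2 the improvements score 5 + 7.5 + 5 = 17.5 if read as relative changes. Read as absolute changes, assuming a 0–3 CHAQ range, they score at most 2.5 + 5 + 7.5 = 15. Both fall below the adult minimal cutpoint of 20 and the pediatric one of 30. This also stands, but it does not settle the primary count.

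The physician rating makes same-visit overlap less likely, and the intervals for 5/10 and 6/10 overlap heavily. Both are true.

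A reader might go further and infer that worsening patients are held in the trial and are treatment failures by definition. The documents do not say so: Section 9.0 encourages patients to stay, says that they could be termed failures, and allows for removal.

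A reader might also infer that any earlier worsening should bar a response. That does not fit the design. The endpoint is status after 24 weeks, and the week-12 dose option is open to patients without 5% improvement, including those rated as worse. A patient who recovers under that option is within the planned treatment.

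**Conclusion.** The gap is real but narrower than a general conflict between the two rules. At week 24 the DOI and the worsening classification can both hold, mainly through branch 2; through branch 1 only for MMT worse by 20% to less than 25% on the Section 2.1 wording; and not through branch 3. Separately, a week-24 DOI reached after alternative therapy or a corticosteroid increase for worsening counts as a response, because Section 15.0 is silent. The same-visit result assumes a common baseline reference and a physician rating of at least moderately worse.

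How often either route would occur cannot be derived from the documents. The size that can be stated is 10 percentage points per patient (1/10), enough to decide between 5/10 and 6/10. This is a cheap improvement to the plan, not a flaw that invalidates it.

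**What to change.** State in Sections 2.1, 3.1 and 15.0 that, for the 6-of-10 count, a patient is a non-responder if either:

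- the Section 9.0/Appendix F worsening criteria are met at week 24; or
- before week 24 the patient received alternative therapy, or a corticosteroid increase, because of disease worsening.

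Report the unmodified published DOI count beside it. State that worsening at an earlier visit alone, or use of the week-12 abatacept dose option, is not automatic non-response. Name the reference visit for the worsening criteria, and reconcile the muscle-strength wording (and the 25% boundary) between Section 2.1 and Appendix D1.

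**Cost.** A few lines of text. The core measures, the physician's outcome rating and concomitant medication are already recorded at the follow-up visits; the reason for a treatment change would need a field if the case report form lacks one. The modified count can only equal or fall below the published DOI count, and it departs from the published definition, which is why both are shown. This is an analysis rule only: no dose, rescue or stopping rule changes.
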